1 PROTOCOL SUMMARY

1.1 SYNOF	SIS
-----------	-----

ir Mejor Study: Randomized Controlled Trial of a Culturally Adapted I Program of Cognitive-Behavioral Therapy for Insomnia for Spanish ting Latina/o Primary Care Patients 1274 parallel-group, single-site, 2-arm Hybrid Type-1 effectiveness- montation study. We will encoll 200 adults with positive chronic
4274 parallel-group, single-site, 2-arm Hybrid Type-1 effectiveness- montation study. We will encoll 200 adults with positive chronic
parallel-group, single-site, 2-arm Hybrid Type-1 effectiveness-
Initiation study . We will enfold 200 aduits with positive chronic mia screen into a superiority randomized controlled trial to compare the iveness of a culturally-adapted Spanish-language digital program of CBT-I Somryst (+ usual care, and sleep hygiene brochure) versus minimally need usual care (mEUC) (usual care + sleep hygiene brochure). Follow-up sments of insomnia symptoms and of secondary outcomes will be acted at post-intervention (9 weeks) and 6 months follow-up by a staff per blinded to group assignment. Sleep duration and sleep efficiency will sessed with actigraphy at baseline (prior to randomization) and at post- rention (9 weeks). Patients will be randomly assigned in a 1:1 ratio to the Culturally Adapted digital CBT-I program (Somryst) or minimally need Usual Care (mEUC) condition. Randomization will be generated by a uterized random-number sequence and held by the study statistician. equence will be unknown to research assistants enrolling patients. Our ry hypothesis is that patients randomized to the Somryst treatment tion will experience a greater improvement (from baseline) in the nuia Severity Index (ISI) at post-intervention (9 weeks) compared to those imized to mEUC, and scores will continue to be better than mEUC nts at 6 months post-intervention. The null hypothesis is that there will difference in the ISI scores between patients randomized to the Somryst
nent versus those assigned to mFUC.
rimary objective of the proposed study is to examine the effectiveness of urally adapted digital CBT-I program compared to minimally enhanced care (mEUC) on primary outcomes: reduction in insomnia symptoms at 9 s, and 6 months post-intervention using a standard scale. Secondary mes will include quality of life, daytime sleepiness, satisfaction with care, quality, and self-reported and actigraphy-assessed wake after sleep as well as self-reported sleep onset latency at post-intervention. ratory outcomes will include actigraphy-assessed sleep duration and sleep ency.

Endpoints:	Primary Endpoint: Insomnia symptoms will be assessed at baseline, at 9 weeks (post-intervention) and at 6 months post-intervention follow-up using the ISI. Secondary Endpoints: Health-related quality of life will be assessed through the validated Short-Form 12 (SF-12), Day time sleepiness will be measured with the 8-item Epworth Sleepiness Scale at baseline, at 9-weeks, and 6- months; Satisfaction with care will be measured using a question adapted for this trial asking patients to rate the quality of professional care they have received for their symptoms of insomnia at post-intervention and 6 -months; Wake after sleep onset will be measured with self-report and actigraphy, and sleep onset latency will be measured with self-report at post-intervention. Sleep quality will be measured with the PSQI at baseline, 9 weeks, and 6- months. Sleep duration and sleep efficiency will be measured continuously and unobtrusively for 14 days at baseline and for 14-days post-intervention using the ActiWatch SpectrumPRO, an actigraphy-based device.
Study Population:	Two hundred Latina/o adult patients from primary care clinics affiliated with Columbia University Irving Medical Center and New York Presbyterian Hospital (the Ambulatory Care Network) that serves underserved communities across New York City will be enrolled into the study. Patients will be Spanish speaking or bilingual (English and Spanish) adults with moderate to severe insomnia symptoms as documented on initial eligibility screen, who are interested in receiving digital care to improve their insomnia in Spanish.
Phase or Stage: Description	Phase III trial
of Sites/Facilities Enrolling	Patients will be recruited through flyers, email, telephone, and primary care provider referrals from primary care clinics affiliated with Ambulatory Care
raiticipants.	Network (ACN) of New York Presbyterian Hospital (NYPH). The catchment areas
	are the ACN clinics of NYPH, which serve 1.4 million individuals in NYC, including
	low socioeconomic and racially/ethnically diverse communities in NYC such as
	Washington Heights, Inwood, Harlem, and the Southwest Bronx, as well as
	geographically broader communities, including Queens. This is a single-site
	study and the site is not outside of the United States.

18 May 2022

Description of Study	Study candidates who meet initial eligibility criteria and consent to participate
Intervention/Experimental	will be invited for an online virtual or in-person visit dependent on participant
Manipulation:	preference where they will complete a baseline sociodemographic and
	psychosocial survey battery, and be asked to complete a daily sleep diary for
	14 days and to wear an actigraph (Actiwatch) that will be mailed to them to
	capture continuous objective sleep data on sleep duration and sleep efficiency
	for 14 days. Participants will be asked to return their actiwatch via mail. After
	completing the baseline assessment, patients will be randomly assigned in a
	1:1 ratio to either the intervention condition (Somryst) or the comparator
	condition (Minimally Enhanced Usual Care (mEUC). Patients in the intervention
	group will receive the culturally adapted digital CBT-I (Somryst), usual care by
	their PCP and a sleep hygiene brochure. Patients will also be trained on how to
	record their daily sleep diaries using a smartphone diary; and will receive
	prompts on their smartphones or emails to remind them when to complete
	the daily sleep diaries. Patients randomized to the control group will receive
	minimally enhanced usual care (mEUC), which will include the usual care
	provided by their PCP, and an informational brochure on sleep hygiene.
	Patients in both groups will have their insomnia severity assessed again at 9-
	weeks post-intervention and at 6-months follow-up. Patients in both groups
	will also wear the Actiwatch Spectrum Pro to objectively assess sleep for 2
	weeks after enrollment and again at the post-intervention assessment.
Study Duration:	8 months
Participant Duration:	8 months
-	

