1.3 SCHEDULE OF ACTIVITIES

After the cultural adaptation of Somryst developed in study 1, we will then enroll 200 patients into the RCT to compare the effectiveness of the culturally adapted digital program of CBT-I (Spanish Somryst) to minimally enhanced usual care and to determine cost-effectiveness of the intervention. Summary data from our pilot study indicate that 94 people were screened over 6 months, 52% were found eligible, and 71% completed the study. In particular, our screening in one primary care clinic over two months resulted in 22 people screened, 77% were eligible, and 71% completed the first focus group. Our pilot data indicate that we are able to screen 8 patients/month and enroll patients/month from one clinic and that an accrual rate of 12/month from multiple clinics is reasonable. The specific list of measures and schedules of activities are represented in Table 1.

Table 1. List of Measures and Schedule of Activities

	Screening/ Enrollment	Baseline	Pre-Tx	Treatment	Post-Tx (9 weeks)	6-mo Follow -Up
Procedure/Assessment/Follow -Up Windows	Virtual or in person	Virtual or in person	14 days before tx	Through Week 9 of Study	Post-Tx (9 weeks)	6-mo Post- Tx
Sociodemographic information	Х					
Insomnia Severity Index	Х	Х		Х	Х	Х
Informed Consent/Enrollment	Х					
Permission for Future Contact and Use	х					
Sleep and Depression Medicines	х				Х	Х
Sleep Disorder	х					
CAGE Assessment	Х					
Assessment for Bipolar/Psychosis/ Schizophrenia	Х					
Health Care Coverage	Х					
Assessment for Cognitive Impairment	Х					
Language Proficiency	х					
Technology Use	Х					
Referral/Contact Information	Х					
Randomization				Х		
Generalized Anxiety Disorder (GAD-7)		Х		Х	Х	Х
Epworth Sleepiness Scale (ESS)	Х	Х			Х	Х

			1	-	1
Pittsburgh Sleep Quality Index (PSQI)	Х			X	X
Quality of Life (SF-12)	Х			Х	Х
Satisfaction with Care (PACIC)	Х			Х	Х
Health Literacy	Х				
Penn State Worry Questionnaire (PSWQ)	X				
Personal Health Questionnaire Depression Scale (PHQ-8)	Х		х		
Health Care Utilization	Х			Х	Х
Medical History	Х				
Dysfunctional Attitudes and Beliefs about Sleep (DBAS-16)	Х			X	Х
Hospitalization				Х	Х
Acceptability and satisfaction with intervention				X	
Actigraphy		Х		Х	
Usability and Net promoter questionnaire				Xa	
Sleep Diary		Х		Х	
Adverse Events			Х	Х	Х

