5 STUDY POPULATION

5.1 INCLUSION CRITERIA

In order to be eligible to participate in this study, an individual must meet all of the following criteria:

- 1. Provision of signed and dated informed screening consent form
- Stated willingness to comply with all study procedures and lifestyle considerations (see Section 5.3, Lifestyle Considerations) and availability for the duration of the study (8 months)
- 3. Males and females; Age 18-65
- 4. Adults with moderate insomnia symptoms as documented on initial eligibility screen based on validated cut-off for community samples (Insomnia Severity Index Score >10)
- 5. Willingness to adhere to the digital therapeutic treatment (study-app based intervention) or enhanced usual care study regimen
- 6. Be Spanish-speaking or bilingual (English and Spanish) adults
- 7. Self-identify as Hispanic or Latinx
- 8. Report experience of sleep disturbances for at least 3x/week
- 9. Report experience of sleep disturbances for at least 3 months

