5.5 STRATEGIES FOR RECRUITMENT AND RETENTION

18 May 2022

We will enroll 200 Hispanic/Latinx women and men in equal proportion (50% women, 50% men). Participants will be from several racial groups (27% American Indian, 15% Black or African American, and 58% other races or multiple). Participants will be ages 18-65 years old. Participants will be recruited through flyers, email, telephone, and primary care provider referrals from the primary care clinics affiliated with Columbia University Irving Medical Center and New York Presbyterian Hospital (the Ambulatory Care Network) that serves underserved communities across New York City by providing high quality and affordable patient-centered care. Recruitment will be conducted remotely or in person ensuring safety measures are in line with COVID-19 safety guidelines provided by Centers for Disease Control and Prevention and Columbia School of Social Work. All interested patients will complete a standard insomnia questionnaire (the Insomnia Severity Index) to determine study eligibility according to severity of insomnia, and only those patients with a positive insomnia screen who are eligible to participate will be invited for **a remote** study visit, or an in-person visit dependent on participant preference.

For Spanish-speaking patients: We also have developed a range of strategies aimed at racial/ethnic minority patient populations from which we recruit and consent. In particular, we are sensitive to the cultural diversity of our population and appreciative of language barriers, issues that must be addressed for successful recruitment and retention of participants. To accommodate the Hispanic/Latinx community in New York City and the surrounding boroughs, the consent and research participant forms will be in Spanish and written at a 6th grade reading level to ensure suitability across literacy levels. In addition, our hiring practices have been informed by the needs of our population. For our current studies, approximately 75% of our research staff is bilingual and we intend to keep our proportion of Spanish speaking staff at about the same proportion in this project. Hispanic/Latinx participants will be provided with a copy of the consent form and HIPAA form in Spanish. A verbal explanation by a bilingual research member will be provided as well. All ensuing questions will be answered, and participants will then be allowed to sign the consent form and HIPAA form.

Participant incentives

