that may exacerbate sleep difficulties. In addition to these main Cores, there are two other Cores: the Overview and Consolidation/Relapse Prevention Cores. These are critical for each user to receive in order to introduce intervention content and provide a rationale for the intervention (Overview); and integrate the educational, behavioral, and cognitive elements, promote adherence, generalize the information, help the user identify risk situations, and incorporate strategies to reduce relapse (Relapse Prevention).

Somryst relies on user-entered online Sleep Diaries to track progress and to tailor treatment recommendations (i.e., assign a "sleep restriction" window). Intervention content is enhanced through a variety of interactive features, including personalized goal-setting, graphical feedback based on inputted symptoms, animations/illustrations to enhance comprehension, quizzes to test user knowledge, patient vignettes, and video-based expert explanation.

The primary outcome, insomnia symptoms, will be assessed using the ISI at baseline, at post-intervention (9 weeks), and at a 6-month follow-up. Health-related quality of life, sleep quality, secondary outcomes, will also be assessed at the same endpoints as ISI. Daytime sleepiness, another secondary outcome will also be assessed at baseline and at the post-intervention (9 weeks), and 6-month follow-up visit. Satisfaction with care and sleep quality will be assessed at baseline and at post-intervention (9 weeks) and 6-months, and sleep duration and efficiency will be assessed 14 days prior to randomization and at post-intervention (9 -weeks).

Comparator Arm: minimally Enhanced Usual Care (mEUC)- (usual care + sleep hygiene brochure) Patients randomized to the mEUC condition will continue to receive the typical standard of care in that clinic from their primary care provider (which may include pharmacotherapy). We have labeled the condition "minimally enhanced" because patients will be provided with a sleep hygiene brochure. Minimally EUC was chosen as the comparator because it is of high clinical relevance, will allow us to determine if the adapted digital CBT-I is superior to usual care, and addresses ethical issues (i.e., identifying but not treating insomnia).⁷⁸ Patients randomized to mEUC will complete assessments on the same schedule as those randomized to the intervention arm.

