6.3 MEASURES TO MINIMIZE BIAS: RANDOMIZATION AND BLINDING

Randomization. After completing the baseline assessment, patients will be randomly assigned in a 1:1 ratio to either the Culturally Adapted Somryst or minimally Enhanced Usual Care (mEUC) condition. Randomization will be generated by a computerized random-number sequence programmed by the study statistician and implemented in the secure, password-protected, encrypted data tracking program. The sequence will be unknown to research assistants enrolling patients.

Blinding. One research staff member (TBN) will be responsible for randomizing participants and so this research assistant and the PI will be unblinded to study condition. Participants will also be unblinded to study condition since treatment conditions will be obvious to them. Research assistants conducting the post-intervention (9 weeks) and 6-month outcome assessments will be blinded to participants' treatment condition, as this is preferred to minimize risk of bias in outcome ascertainment.

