9.4.2 ANALYSIS OF THE PRIMARY ENDPOINT(S)

Mixed-model RM-ANOVA will be used to estimate and compare the changes in the primary endpoint (ISI) and other patient-important outcomes (e.g., insomnia symptom severity, daytime sleepiness) between Somryst and mEUC. The RM-ANOVA model will include Group (Somryst versus mEUC), Time (baseline, post-intervention and 6-month follow-up), and the Group × Time interaction as fixed factors with an unstructured residuals covariance matrix. This will yield estimates of the within-group means and standard errors at each assessment. Specific interaction contrasts (e.g., Group × Pre-vs-Post Intervention) will be estimated to estimate the magnitude and test the statistical significance of the differential change in insomnia symptoms using the Wald χ^2 statistic. We will plot the mean insomnia scores across assessments, stratified by treatment group, to elucidate the nature of the interaction (i.e., whether Somryst resulted in significantly greater improvements [or lesser worsening] than mEUC). If, despite randomization, the two groups differ substantially (p<0.10 after stepdown Bonferroni correction) on one or more sociodemographic or clinical factors assessed at baseline, sensitivity analyses will be performed in which these factors are included as covariates in the RM-ANOVA, in order to rule out the possibility that the results from the primary analyses are attributable to group differences on these factors. The same analyses will be repeated to estimate and compare changes in the primary endpoint and secondary endpoints between Somryst and mEUC at 6-months.

Significance will be evaluated with a two-tailed p value of 0.05. To control for multiplicity, postintervention will be evaluated first and if significant timepoints post-intervention and 6-months followup will be evaluated. In addition, estimated marginal means \pm 95% confidence intervals will be calculated for each assessment point and Cohen's d will be used as an estimate of effect size for the change from baseline to each assessment point.

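### The ISI is measured twice before randomization, but the primary model uses one score and only as an unadjusted change; conditioning on both is a free gain in precision

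*Combined protocol and SAP*

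**What the plan says.** - **Endpoint.** Section 1.1 (Endpoints): "Insomnia symptoms will be assessed at baseline, at 9 weeks (post-intervention) and at 6 months post-intervention follow-up using the ISI".
- **Screening score.** Section 5.5: "All interested patients will complete a standard insomnia questionnaire (the Insomnia Severity Index) to determine study eligibility according to severity of insomnia". The threshold in Section 5.1 is "Insomnia Severity Index Score >10".
- **Baseline score.** Section 6.1.1: "The primary outcome, insomnia symptoms, will be assessed using the ISI at baseline, at post-intervention (9 weeks), and at a 6-month follow-up". In Table 1 (Section 1.3) the row "Insomnia Severity Index" is marked under both Screening/Enrollment and Baseline.
- **Order.** Section 6.3: "After completing the baseline assessment, patients will be randomly assigned in a 1:1 ratio". Both scores therefore precede assignment.
- **Model.** Section 9.4.2 fits Group, Time and Group × Time with an unstructured covariance. The Time levels are "Time (baseline, post-intervention and 6-month follow-up". The tested quantity is the Group × Pre-vs-Post contrast. Covariates enter only in sensitivity analyses, and only if the arms differ at baseline.
- **Power.** Section 9.2 assumes a 3-point difference, an SD of change of 6.0, 200 randomized and 170 followed, for 90% power.

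**The concern.** With free arm means at baseline, the tested contrast is the arm difference in follow-up ISI minus the arm difference in one baseline ISI. All the chance variation in that single score passes into the treatment estimate. A model that conditions on pre-randomization ISI subtracts only the part that predicts follow-up. A second score may improve that prediction, and neither score can be affected by arm.

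What is at stake is the standard error of the primary contrast at 9 weeks, and at 6 months, which is tested only if 9 weeks is significant. Validity is not at stake.

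**Working it through.** **1. The plan's own figure.** Inputs from Sections 9.2 and 9.4.2: difference 3, SD of change 6.0, 170/2 = 85 per arm, two-sided 0.05.

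- SE = 6.0 × √(2/85) = 0.920, and 3/0.920 = 3.26.
- Power = Φ(3.26 − 1.96) = Φ(1.30) = 90.3%.
- In reverse, 90% power needs 85 per arm, or 170, and 170/0.85 = 200.

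The stated 90% reproduces.

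**2. Formulas.** Let S, B and Y be the screening, baseline and follow-up ISI, with equal variances. Let a = corr(B,Y), s = corr(S,Y) and r = corr(S,B). In units of the ISI variance, each analysis has variance:

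- planned change from baseline: 2 − 2a
- conditioning on B only: 1 − a²
- conditioning on S and B: 1 − (a² + s² − 2ars)/(1 − r²)
- change from the mean of S and B: 1 + (1 + r)/2 − a − s

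Dividing by 2 − 2a gives the ratio to the planned contrast. The effective SD is 6.0 × √ratio, entered in the power formula of step 1.

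**3. Assumptions.** The documents give none of a, s or r. I take a = 0.35 to 0.6 and r = 0.5 to 0.9, with r at least as large as a, under two structures. In the equal structure, s = a, so screening predicts follow-up as well as baseline does. In the decay structure, s = r × a, so correlation falls with time. Under decay, the formula for both scores reduces to 1 − a², so screening adds nothing.

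**4. Results (variance ratio; power).**

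| a | r | structure | B only | S and B | mean of S and B |
|---|---|---|---|---|---|
| 0.35 | 0.5 | equal | 0.675; 97.8% | 0.644; 98.2% | 0.808; 95.2% |
| 0.5 | 0.5 | equal | 0.750; 96.4% | 0.667; 97.9% | 0.750; 96.4% |
| 0.5 | 0.7 | equal | 0.750; 96.4% | 0.706; 97.3% | 0.850; 94.2% |
| 0.5 | 0.7 | decay | 0.750; 96.4% | 0.750; 96.4% | 1.000; 90.3% |
| 0.6 | 0.6 | equal | 0.800; 95.4% | 0.688; 97.6% | 0.750; 96.4% |
| 0.6 | 0.6 | decay | 0.800; 95.4% | 0.800; 95.4% | 1.050; 88.9% |
| 0.6 | 0.8 | decay | 0.800; 95.4% | 0.800; 95.4% | 1.025; 89.6% |

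Over this range, conditioning on both scores gives 95.4% to 98.2%. Screening contributes between 0 and 2.2 points (97.6 − 95.4). At a = 0.7, baseline alone gives 94.2%, and both scores give 94.2% (decay) to 97.3% (equal, r = 0.7), a step of up to about 3 points.

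**5. The simple mean.** It loses precision when a − s exceeds (1 − r)/2. Under decay that means a above 0.5. At a = 0.6, r = 0.6: a − s = 0.6 − 0.36 = 0.24, against (1 − 0.6)/2 = 0.20.

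**6. Selection at ISI >10.** This was checked by simulation under equal correlations (assumed unselected mean 12 to 17, SD 5; a 0.4 to 0.6, r 0.5 to 0.7). Conditioning on both gave power of 96.9% to 97.9%, against 95.6% to 97.4% for baseline alone. Truncation reduces what screening adds but does not reverse the gain.

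**The case against.** **One prespecified baseline is an ordinary choice, and the trial is adequately powered on its own terms.** This stands. A reader might infer that the primary analysis is invalid or underpowered. The documents do not support that: the 90% reproduces, and Section 9.2 calls the SD of 6.0 conservative. At the SDs of 4 to 5 it cites, planned power is already 99.8% to 97.5%.

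**The gain from the second score is small.** This also stands. A reader might infer that averaging the two scores cuts variance by 25% and lifts power to 96.4%. That holds only if screening predicts follow-up as well as baseline does. Under decay the mean gains nothing or loses slightly. It would also replace the change-from-baseline endpoint in Sections 3 and 9.1, and reported within-arm changes from baseline would no longer subtract to the primary treatment difference. The ISI covers the past two weeks (Section 8.1), so if the visits fall close together, recall windows overlap and the second score carries little new information.

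**The screening score was used for selection, and rescreening is allowed (Section 5.4).** Selection and regression to the mean act on both arms before assignment and do not bias the arm contrast. Rescreening does require a rule for which score counts.

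**The ESS.** Table 1 marks it at both contacts too, so a reader might infer the same loss. The plan makes no power claim for the ESS, its screening value is truncated by the exclusion at 16 or above, and no gain has been quantified.

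**Conclusion.** The concern holds as an efficiency improvement. A pre-randomization measurement of the primary outcome is collected and not analysed, and the score that is analysed enters without adjustment. Conditioning on both would raise power from 90.3% to about 94% to 98% under the plan's own effect, SD and attrition. Most of that comes from conditioning on baseline; screening is the smaller step and may add nothing.

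The size rests on assumed correlations, equal variances and 85 evaluable patients per arm. The direction is safer: with both scores in the conditioning set, the cost is at most a few degrees of freedom.

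**What to change.** In Section 9.4.2, before outcome data are examined by arm, keep the 9-week and 6-month Group contrasts and condition on both pre-randomization ISI scores in one of two ways:

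1. Model the two follow-up scores, with screening and baseline ISI as covariates, each with a Time interaction.
2. Keep the repeated-measures model, with screening and baseline as pre-randomization Time levels whose means are constrained equal across arms. This form also keeps patients without follow-up in the model, in line with the statement in 9.4.2 that all 200 are analysed.

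Adding screening to the planned model as a covariate main effect alone, or as a free fourth Time level with the contrast unchanged, gains essentially nothing. Do not use change from the simple mean of the two scores. For rescreened patients, specify the qualifying screening score.

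The cost is SAP wording and one already-collected value per patient; no new data are needed and the target of estimation is unchanged. Extending this to the ESS is optional.
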